Electrical muscle stimulation for the treatment of functional posterior shoulder instability – A randomized multicentric study

Clinical Study Protocol

Short Title: EMS Study

Study Type:	Prospective randomized controlled trial
Principal Investigator:	PD Dr.med.univ. [name]
	Center for Musculoskeletal Surgery (CMSC)
	Charité University Hospital Berlin
	[name]
	Email: [contact]
Protocol Version and Date:	4.0 08.04.2020

STUDY SYNOPSIS

Sponsor	PD [name], Charité Berlin					
Sponsor - Representative	[name]. [name]					
Study Title:	Electrical muscle stimulation for the treatment of functional posterior shoulder instability – A randomized multicentric feasibility study					
Trial registration:	http://www.isrctn.com/ISRCTN10085480					
Background and Rationale:	Functional posterior shoulder instability (FPSI) is a force imbalance of stabilizing shoulder muscles which mainly affects teenagers and young adults with severe implications on shoulder function. Severily restricted shoulder function and symptoms such as pain, loss in range of motion due to weakness or blockage that inhibits any further movement as well as a strong feeling of instability are reported by the affected patients. Even though surgical treatment is effective in structural posterior shoulder instability, patients suffering from FPSI should not be treated surgically since it often does not lead to the desired stabilization of the shoulder joint but instead to severe pain, movement restriction, as well as early glenohumeral degenerative changes. Current gold-standard treatment consists of physiotherapy including core exercises, coordination training, strengthening exercises as well as training with biofeedback. However, conventional physiotherapy as well as muscle training therapy is also often ineffective. In a multicentric prospective randomized controlled trial we would like to objectively assess a promising new EMS (Electrical muscle stimulation)-based treatment concept which was evaluated at our institution in a prospective pilot trial involving 24 cases with previously unsuccessful conventional physiotherapy treatment of FPSI.					
Objective(s):	The primary objective is to demonstrate that the EMS based therapy shows a better clinical effect than the convential state-of-the art physiotherapy treatment of functional posterior shoulder instability.					
Outcome(s):	Primary Parameter:					
	- WOSI (Western Ontario Shoulder Instability Index)					
	Secondary Parameter:					
	 SSV (Subjective Shoulder Value) ROM Strength measurement (Flexion/Abduction/Rotation) Impairment of daily activities Sports impairment Pain level Satisfaction level with treatment 					
Study design:	Prospective, randomized, controlled, optional crossover study					

Inclusion / Exclusion criteria:	Key inclusion criteria: - Non-controllable positional functional posterior shoulder instability
	 Key exclusion criteria: < 14 years multidirectional instability static posterior instability/migration connective tissue disease degenerative joint disease structural defects visible on pre-treatment MRI Any acquired glenoid bone defect Glenoid dysplasia with more than 10° of retroversion (of cartilagineous surface) according to Imhoff et al.⁷ Convex cartilagineous glenoid articular surface Static posterior glenohumeral decentering >55% according to Walch et al.¹⁸ Degenerative changes (any visible cartilage damage or OA) neurological disorder or nerve injury existing pain syndrome (defined by pain at rest or during motion which is not caused by dislocation but impedes physiotherapeutic training and/or EMS) non-tolerance of EMS treatment (e.g. cardiac pacemaker) previous participation in a pathology-specific standardized EMS or physiotherapy protocol
Measurements and procedures:	Follow-up per patient (time after start of the treatment) : Baseline (Inclusion), 0 weeks (Start treatment), 6 weeks, 3 months, 6 months and 12 months Duration of intervention per patient : 6 weeks
Study Product / Intervention:	Experimental intervention: electrical muscle stimulation based therapy protocol
Control Intervention (if applicable):	Control intervention : conventional state-of-the art physiotherapy protocol
Number of Participants with Rationale:	There will be a total of 88 patients included. Rationale: See Statistical Considerations
Study Duration:	30 months
Study Schedule:	01/20 First-Participant-In (planned) 07/22 Last-Participant-Out (planned)

Study Centre(s):	It is a multicentric, multi-national study.					
	N=6 clinics					
	 Clinics: Charitè University Hospital, Berlin, Germany (Leadclinic) ATOS Clinic, Munich, Germany Hannover Medical School (MHH) – DIAKOVERE Annastift – Department of Orthopaedic Surgery, Hannover, Germany St. Vincentius Clinic, Karlsruhe, Germany University Hospital Düsseldorf, Department of Orthopaedics and Trauma Surgery, Düsseldorf, Germany Schulthess Clinic, Zurich, Switzerland 					
Statistical	Sample Size:					
Considerations:	The calculated sample size for a power of 80%, an alpha error probability of 5%, and an estimated effect size of 0,8 is 52. The effect size was calculated according to Cohen by dividing the minimally clinically important difference of the WOSI (10,4%) by the expected standard deviation of the WOSI among the study participants (13%) based on the pilot trial results.					
	When accounting for an expected drop-out rate of approximately 20% due to non-compliance or loss to follow-up 66 patients need to be assigned to the trial. Due to the strict exclusion criteria with an expected exclusion rate of 25% approximately 88 patients need to be assessed for eligibility.					
	In the pilot trial the adherence rate to the EMS treatment was 88%. A similar compliance rate is expected for both intervention groups of the proposed project. The rate of loss to follow-up is expected to be low considering the short follow-up period until reaching the primary endpoint at time-point T2 (3 months after the beginning/6 weeks after the end of the intervention). The expected combined drop-out rate due to lack of compliance with treatment or loss to follow-up is 20%.					
	Primary Analysis					
	The analysis of the primary outcome parameter (WOSI at 3 months) will be performed using an independent sample T-Test or linear regression with WOSI as the dependent variable and treatment intervention and baseline factor(s) as the independent variable depending on the need for statistical adjustment. The strength of effect will be presented as the mean group difference along with its 95% confidence interval. A random-effect model will be used to account for center effect.					
	Secondary Analyses					
	All secondary analyses will be explorative. Secondary outcome variables will be analyzed using univariable random-effect logistic (categorical variables) or linear (continuous variables) regression. Multivariable regression will be conducted depending on the need for adjustment of baseline prognostic factors. Significance level is set to 0.05.					

GCP Statement:	This study will be conducted in compliance with the protocol, the current version of the Declaration of Helsinki, the ICH-GCP or ISO
	EN 14155 (as far as applicable) as well as all national legal and regulatory requirements.

STUDY SCHEDULE

Table 1: Schedule of examination time points and data collection (mo = months, w = weeks)

	Screen Visit	Intervention	0 w	6 w (± 1w)	3 mo (±1w)	4.5* mo (±1w)	6 mo (±2w)	12 mo (± 2w)	
Inclusion/Exclusion	х								
Consent/Randomizatio	х								
n Demographics Video Pathology History Western Ontario Shoulder Instability Index (WOSI)	x x x		x	x x	x x	x x	x x	x x	
Subjective Shoulder Value (SSV)	v		×	v	v	v	v	V	
Clinical Examination (Strength/ROM) Impairment of daily activities	x x x		x x x	x x x	x x x	x x x	x x x	x x x	
Sports impairment	х		х	х	х	х	х	х	
Pain level	х		х	х	х	х	х	Х	
Satisfaction level with treatment Adverse Events / Complications	x	x	x x	x x	x x	x x	x x	x x	

Follow-up time points and window¹

* = only if crossover has been made

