6.2.1 Randomisation

A randomization sequence will be generated electronically using Stata (StataCorp LP, Texas USA) separately for each participating centers for up to X patients and loaded within an online study database in REDCap² (Research Electronic Data Capture) for automatic concealed allocation. Block-randomization with blocks of 2 and 4 will be used to minimize the risk of unequal group sizes. The randomization process allows to divide the study participants into two cohorts of comparable characteristics. We will compare these cohorts with regards to potential confounding factors before the outcome analyses and adjust statistically for any observed imbalance as appropriate.

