10.2 Determination of Sample Size

The calculated sample size for a power of 80%, an alpha error probability of 5%, and an estimated effect size of 0,8 is 52. The effect size was calculated according to Cohen by dividing the minimally clinically important difference of the WOSI (10,4%) by the expected standard deviation of the WOSI among the study participants (13%) based on the pilot trial results. The software used to calculate the sample size was G*Power (HHU Duesseldorf, Duesseldorf, Germany). When accounting for an expected drop-out rate of approximately 20% due to non-compliance or loss to follow-up 66 patients need to be assigned to the trial. Due to the strict exclusion criteria with an expected exclusion rate of 25% approximately 88 patients need to be assessed for eligibility.

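### The synopsis gives 88 as the number of patients included, but the protocol's own derivation makes 88 the number screened and 66 the number assigned

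*Protocol*

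**What the plan says.** The synopsis row headed Number of Participants with Rationale reads: "There will be a total of 88 patients included", and it points to the statistical considerations for the rationale. That rationale stands a few rows further down the same synopsis table, under Statistical Considerations, and is repeated in section 10.2. Three numbers appear there, each with its own meaning:

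- For the analysis: "The calculated sample size for a power of 80%, an alpha error probability of 5%, and an estimated effect size of 0,8 is 52".
- After allowing for about 20% drop-out: "66 patients need to be assigned to the trial".
- After allowing for a 25% exclusion rate: "approximately 88 patients need to be assessed for eligibility".

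Section 6.2 sets 1:1 allocation. Sections 7.3 and 8.4 say that patients who withdraw are not replaced. Section 6.2.1 describes the randomisation list as generated "separately for each participating centers for up to X patients", with the X not filled in.

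**The concern.** The row that a reader consults for the size of the trial gives 88, and the text it cites as its reason gives 66 for the same quantity. The synopsis thus disagrees with itself as well as with section 10.2. Because withdrawn patients are not replaced, the number randomised is the size of the trial and should be stated once and consistently.

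If both figures stay, a site or committee that reads only the synopsis will plan for a third more patients than the calculation calls for. Whichever number is enrolled, the final report can be held against the other: 66 is 25% below the synopsis figure (22/88), and 88 is 33% above the derived figure (22/66).

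**Working it through.** **Inputs.** From section 10.2: difference to detect 10.4 percentage points on the WOSI, standard deviation 13 points, alpha 5%, power 80%, drop-out 20%, exclusion rate 25%. From section 6.2: allocation 1:1. Section 10.2 does not say whether alpha is one-sided or two-sided; two-sided is assumed here because it reproduces the stated figure.

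**Step 1, patients for analysis.** d = 10.4/13 = 0.8. For a two-sample t-test (noncentral t), two-sided alpha 0.05 and 80% power, the smallest size is 26 per arm, or 52 in total, with power 0.807. This matches the stated 52. A one-sided test would give 21 per arm (42), and the normal approximation 25 per arm (50), so the two-sided t-test is what was used.

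**Step 2, patients assigned.** 52/(1 − 0.20) = 65. Rounded up to an even number for 1:1 allocation this is 66, the stated figure.

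**Step 3, patients screened.** 66/(1 − 0.25) = 88 exactly, again the stated figure. Starting from 65 would give 65/0.75 = 86.7, so the 88 was built on the 66.

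**Step 4, what 88 contains.** 88 × 0.25 = 22 patients expected to be excluded, and 88 × 0.75 = 66 left to assign.

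**Step 5, what 88 included would imply.**

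| | 66 randomised | 88 randomised |
|---|---|---|
| To be screened | 66/0.75 = 88 | 88/0.75 = 117.3, so 118 |
| Left after 20% drop-out | 66 × 0.8 = 52.8 | 88 × 0.8 = 70.4 |
| Power at d = 0.8 | 0.807 (26 per arm) | 0.910 (35 per arm) |

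None of the figures that would go with 88 randomised (118 screened, about 70 analysed, 91% power) appears in the protocol. Every figure that goes with 66 does.

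**The case against.** The best defence is that this is one loosely worded line that sends the reader straight to its own correction. The row names its source, the source is in the same table, and the source is clear. All of that stands. The arithmetic is correct, nothing in the protocol is powered for 88, and the primary analysis and the 52 patients it needs are unaffected.

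A second defence is that included may here mean consented and screened. Section 7.3 starts participation at the signing of consent, the study schedule puts eligibility and consent at the same screening visit, and section 7.1 speaks of excluding a participant. This reading is possible but not natural. The row counts participants, the synopsis attaches the word inclusion to the baseline visit, and sections 3.6 and 7.1 use included for patients who enter the study, as opposed to those whom the exclusion criteria remove. Most readers would take 88 as enrolled.

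Three stronger readings are tempting, and the protocol does not support them:

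- *That nothing fixes when recruitment stops.* The synopsis and section 10.2 both give 66 to be assigned, and replacement is ruled out. The target is stated, although it is not worded as a cap and the synopsis row contradicts it.
- *That the sponsor keeps a choice between 66 and 88 in the light of the results.* The trial is open-label, and section 2.6 allows early termination for evidence of benefit or harm. But the protocol provides for no comparison at 66 followed by a decision to go on, and the discretion in section 2.6 exists whatever the synopsis says.
- *That the unfilled X in section 6.2.1 leaves the size open.* It is the maximum length of each centre's list. Lists may be longer than the expected enrolment when centres recruit unevenly, so filling in X would not set the overall number, and leaving it blank does not make 88 the target.

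**Conclusion.** The point holds as a mislabelled figure. The synopsis presents the screening number as the enrolment number, 22 patients or 33% above the 66 that the protocol derives. The sample-size calculation reproduces at every step, and 66 randomised gives the stated 80% power under the protocol's own assumptions (d = 0.8, 20% drop-out), so power is not at risk. The conclusion rests on reading included as enrolled and assigned as randomised, which is how the protocol otherwise uses the words. The two-sided test and the rounding of 65 to 66 are inferred from the match with the stated figures.

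The correction is small, but it should be made, because the number of participants is a figure on which the trial relies and it is wrong as written. What registries or ethics committees were told cannot be seen from the protocol and forms no part of this conclusion.

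**What to change.** In the synopsis row, replace the statement of 88 with: 66 patients randomised (33 per arm), from about 88 assessed for eligibility. State once, in section 10.2, that enrolment closes when 66 patients have been randomised across all centres.

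If the sponsor really intends to randomise 88, the correction goes the other way: section 10.2 and the matching synopsis text must be revised to justify 88, with about 118 to be assessed for eligibility at the same exclusion rate.

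The X in section 6.2.1 should be completed as a separate editorial item; a fixed list length per centre is not needed to settle the trial size.

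The cost of the first option is a line or two of text, carried into any document that copied the 88. It needs no extra patients and no change to the analysis.

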2. ETHICAL AND REGULATORY ASPECTS

2.1 Study registration

The study has been registered in the ISRCTN registry, a clinical trial registry recognised by WHO and ICMJE: http://www.isrctn.com/ISRCTN10085480

2.2 Competent Ethics Committee (CEC)

Each investigator has to seek the approval from the CEC for the conduction of the clinical study

The reporting duties (all changes in the research activity and all unanticipated problems involving risks to humans; including in case of planned or premature study end and the final report) will be followed as written in the applicable law.

No changes are made to the protocol without prior Sponsor and CEC approval, except where necessary to eliminate apparent immediate hazards to study participants.

Premature study end or interruption of the study is reported within 15 days. The regular end of the study is reported to the CEC within 90 days, the final study report shall be submitted within one year after study end.

2.3 Ethical Conduct of the Study

The study will be carried out in accordance to the protocol and with principles enunciated in the current version of the Declaration of Helsinki, the guidelines of Good Clinical Practice (GCP) issued by ICH, the European Regulation on medical devices 2017/745 and the ISO Norm 14155 and ISO 14971, and the national regulatory authority's requirements. The CEC and regulatory authorities will receive annual safety and interim reports and be informed about study stop/end in agreement with local requirements.

2.4 Patient Information and Informed Consent

The investigators will explain to each participant the nature of the study, its purpose, the procedures involved, the expected duration, the potential risks and benefits and any discomfort it may entail. Each participant will be informed that the participation in the study is voluntary and that he/she may withdraw from the study at any time and that withdrawal of consent will not affect his/her subsequent medical assistance and treatment.

The participant must be informed that his/her medical records may be examined by authorised individuals other than their treating physician.

All participants for the study will be provided a participant information sheet and a consent form describing the study and providing sufficient information for participant to make an informed decision about their participation in the study.

The participants get enough time (min 24h) whether to participate or not.

The formal consent of a participant, using the approved consent form, must be obtained before the participant is submitted to any study procedure.

The participant should read and consider the statement before signing and dating the informed consent form, and should be given a copy of the signed document. The consent form must also be signed and dated by the investigator (or his designee) at the same time as the participant sign, and it will be retained as part of the study records.

2.5 Participant privacy and confidentiality

The investigator affirms and upholds the principle of the participant's right to privacy and that they shall comply with applicable privacy laws. Especially, anonymity of the participants shall be guaranteed when presenting the data at scientific meetings or publishing them in scientific journals.

Individual subject medical information obtained as a result of this study is considered confidential and disclosure to third parties is prohibited. Subject confidentiality will be further

ensured by utilising subject identification code numbers to correspond to treatment data in the computer files.

2.6 Early termination of the study

The Sponsor may terminate the study prematurely according to certain circumstances, for example:

- ethical concerns,
- insufficient participant recruitment,
- when the safety of the participants is doubtful or at risk, respectively,
- alterations in accepted clinical practice that make the continuation of a clinical trial unwise,
- early evidence of benefit or harm of the experimental intervention

2.7 **Protocol amendments**

Substantial amendments are only implemented after approval of the CEC.

Under emergency circumstances, deviations from the protocol to protect the rights, safety and well-being of human subjects may proceed without prior approval of the sponsor and the CEC. Such deviations shall be documented and reported to the sponsor and the CEC as soon as possible.

All non-substantial amendments are communicated to the CEC within the Annual Safety Report (ASR).

The PI or his designee has the responsibility to amend the protocol or to provide suggestions for a protocol amendment. He is also responsible to communicate these modification to its competent persons.

3. BACKGROUND AND RATIONALE

3.1 Background and Rationale

Functional posterior shoulder instability (FPSI) is a force imbalance of stabilizing shoulder muscles which mainly affects teenagers and young adults with severe implications on shoulder function. Patients with FPSI suffer from repetitive posterior dislocations every time the shoulder passes a particular phase of movement in the mid-range of motion. Severily restricted shoulder function and symptoms such as pain, loss in range of motion due to weakness or blockage that inhibits any further movement as well as a strong feeling of instability are reported by the affected patients. Extreme limitations during daily and sporting activities as well as the "freakish looking dislocations" can lead to stigmatization among peers and emotional stress for the affected patients.¹⁴ The estimated prevalence of this often under- and misdiagnosed pathology is around 0.05% of the population⁵ and might be even higher according to more recent studies.¹² Even though surgical treatment is effective in structural posterior shoulder instability, patients suffering from FPSI should not be treated surgically since it often does not lead to the desired stabilization of the shoulder joint but instead to severe pain, movement restriction, as well as early glenohumeral degenerative changes.^{3; 6; 9; 11; 17} Current gold-standard treatment consists of physiotherapy including core exercises, coordination training, strengthening exercises as well as training with biofeedback.^{8; 17} However, conventional physiotherapy as well as muscle training therapy is also often ineffective. In daily clinical practice patients affected by FPSI typically visit several shoulder specialists and physiotherapists and after years of unsuccessful conservative treatment finally undergo a salvage surgical stabilization attempt with often worse outcome than before.¹⁴ A skillful neglect has been proposed as the alternative treatment option as symptoms may regress after several years.^{6; 11} However, this waiting approach seems not applicable in clinical practice since the affected patients are young and suffer extensively

from their functional restrictions and their social implications. The ineffectiveness of available treatment options and the helplessness of shoulder specialists confronted with this pathology even led to the dismissal of FPSI as attention seeking behavior or even psychiatric condition in the past⁴ which further increased the disease burden and social stigmatization of the patients suffering from FPSI.

In a multicentric prospective randomized controlled trial we would like to objectively assess a promising new EMS-based treatment concept which was evaluated at our institution in a prospective pilot trial involving 24 cases with previously unsuccessful conventional physiotherapy treatment of FPSI.¹³ For the patients themselves this new treatment concept potentially could represent a true "game-changer" that might free them of the burden of FPSI.

For the examined pathology there is no guideline regarding recommended outcome measurements or core outcome sets. The Western Ontario Shoulder Instability Index (WOSI) which is a shoulder instability-specific subjective outcome measurement with proven high validity, reliability, and responsiveness¹⁰ recommended for the evaluation of shoulder instability¹⁵ will serve as main outcome measurement. The WOSI covers four categories: physical symptoms (10 items); sports, recreation, and work (4 items); lifestyle (4 items); and emotions (3 items). The reason to choose a subjective outcome measurement is the fact that 1) the patients' own perception of their shoulder function is a key factor to determine the success of treatment,¹⁶ 2) a comprehensive, valid, and reliable objective clinical or radiographic outcome measurement in this highly-dynamic pathology is not obtainable, and 3) objective clinical outcome measurements might slightly vary between participating centers despite standardization. Secondary outcome measures of the proposed trial include the Subjective Shoulder Value (SSV), impairment of daily activities, sports Impairment, pain level, satisfaction level with treatment, range of motion, and strength. Data collection will include questionnaires independently completed by the patients for subjective outcome measures and standardized clinical examinations by physicians for objective outcome measurements.

